### **4.4.2 Missing Data**

No substitution of missing data will be used in laboratory measurements, vital signs, physical examinations and subject and graft status.

In case of partially missing adverse event start dates, the start dates will be imputed by comparing to the implantation date of HAV so that the corresponding AEs will be made treatment-emergent whenever possible, unless the available partial date information clearly indicates that the event happened before implantation. The general rule of imputation is to assign the first day of a month for a missing day and the first month of a year for a missing month when applicable.

For interventions, if the date of a procedure has a missing day, the first day of that month will be assigned for the missing day unless the partial date has the same year and month as the implantation date, in which case, the day of the implantation will be assigned.

For a partially missing initial renal replacement therapy date, the last day of the month will be assigned for the missing day and no imputation will be performed if both month and day are missing.

### **4.4.3 Spurious Data Points**

Data points that appear to be spurious will be investigated and queried for possible resolution. Data points that are not resolved through queries will be included in the statistical analysis of the data as well as the data listings. Statistical analysis may also be performed with such apparently spurious data excluded as a sensitivity analysis to determine the impact of that data on the study results.

### **4.5 Data Derivations and Transformations**

Not applicable.

## **5. STUDY SUBJECTS**

### **5.1 Disposition of Subjects**

A table of frequency counts and percentages of all enrolled subjects will be provided for the ITT set. Subject completion status and reasons for study discontinuation will be tabulated. A by-subject listing will be provided.

### **5.2 Protocol Deviations**

Distribution for the types of protocol deviations and the number of subjects that deviate from the protocol will be tabulated using the ITT set. A listing of all major protocol deviations will be provided.

### **5.3 Demographic Characteristics**

Descriptive statistics will be used to summarize the demographic characteristics (gender, race, ethnicity, height (cm), weight (kg), and Body Mass Index (BMI) for the ITT set.

$$\text{BMI} = [\text{Weight (kg)}] / [\text{Height (m}^2\text{)}]$$

A by-subject listing of demographic characteristics will be provided.

#### **5.4 Baseline Characteristics**

Baseline characteristics including duration of end-stage disease, number and types of previous accesses, kidney transplant history, smoking history, etc. will be summarized for the ITT set using descriptive statistics. A by-subject listing will be presented.

#### **5.5 Medical History**

All medical conditions and procedures will be classified by system organ class (SOC) and preferred term (PT) using the Medical Dictionary for Regulatory Activities (MedDRA). The number and percent of subjects with each medical condition and surgical procedure will be presented for each SOC and PT using the ITT set.

#### **5.6 Prior and Concomitant Medications**

Prior and concomitant medications will be coded using World Health Organization (WHO) drug classifications. The number and percent of ITT subjects using prior and concomitant medications will be tabulated by Anatomical, Therapeutic, and Chemical (ATC) class and by preferred name. A listing of all medications recorded in the database will be provided.

### **6. EFFICACY ANALYSES**

The status of Primary Patency, Primary Assisted Patency, and Secondary Patency will be assessed by the PI at Month 3, Month 12, and the end of the study. The patency status and the date of loss of patency will be recorded in the eCRF and used for the time-to-event analysis.

#### **6.1 Primary Efficacy Endpoints and Analyses**

The primary efficacy endpoints are the time to loss of Secondary Patency, Primary Patency, and Primary Assisted Patency when the last subject completes 3 months of follow-up. The analysis of primary efficacy endpoints will use the censoring rules described in Section 4.4.1.

In order to provide descriptive summary statistics that are of interest, point estimates and 95% confidence intervals for patency (Primary, Primary Assisted and Secondary) survival probabilities will be provided using Kaplan-Meier (K-M) method.

The following K-M estimates will be provided:

- 25th, 50th (i.e., median) and 75th K-M percentiles with 95% Cis, if applicable
- Number and percent of subjects censored/not censored
- K-M estimates of the proportion of subjects with event-free

#### **6.2 Secondary Efficacy Endpoints and Analyses**

Secondary efficacy analyses on Primary/Primary Assisted/Secondary patency and intervention rate through 36 months of follow-up will be carried out on the ITT set.

## *Humacyte CLN-PRO-V011 Statistical Analysis Plan v1.0*

The time to loss of Primary/Primary Assisted/Secondary patency will be analyzed by K-M method as described in Section 6.1. The K-M estimates of the proportion of subjects event-free at 6, 12, 24, and 36 months will be provided.

Interventions include whatever is done at one session. For example, thrombectomy + angioplasty at one session would be considered as one intervention. Summaries for interventions required that successfully achieved/maintained Secondary Patency will include:

- Number of interventions per subject
- Rate of interventions defined as the number of interventions per subject per year while the HAV is patent (i.e. has not been abandoned). Results will be provided for Day 0 to Month 12 and overall (Day 0 to total follow-up period).
- The number and percent of subjects with each of reasons for interventions
- The number and distribution of thrombectomies, angioplasties, stents, etc. will be analyzed separately

Analysis of histopathological remodeling of HAV will be performed by Humacyte.

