
Primary Endpoints – assessed at 3 months post implantation
	
Safety
 
 
• Adverse events indicating possible mechanical failure or weakness of the HAV (anastomotic rupture, anastomotic bleeding, spontaneous HAV rupture, aneurysm, pseudoaneurysm, abnormal post cannulation hemostasis)
 
• HAV infections
 
• Change from baseline of panel reactive antibody (PRA) and anti-HAV IgG levels (at 2 months)
 
• All adverse events (AEs)/serious adverse events (SAEs) and adverse events of special interest.
 
 
Efficacy
 
 
• Primary / primary assisted/secondary patency
 

Secondary Endpoints – assessed throughout the 36 month follow up
	
Safety
 
 
• Adverse events indicating possible mechanical failure or weakness of the HAV (anastomotic rupture, anastomotic bleeding, spontaneous HAV rupture, aneurysm, pseudoaneurysm, abnormal post cannulation hemostasis)
 
• HAV infections
 
• Change from baseline of PRA and anti-HAV IgG values (at 12 months)
 
• All AEs/SAEs until 12 months post implant, after that only SAEs related to the HAV and adverse events of special interest
 
 
Efficacy
 
 
• Primary/primary assisted/secondary patency
 
• Interventions required to achieve/maintain secondary patency.
 
• Histopathological remodeling of any HAV (based on any
 

	samples collected).
Data Analysis	
This is an exploratory study with no formal hypothesis testing. Data will be summarized using descriptive statistics only.
 
All available data will be summarized and reported in a clinical study report (CSR) when the last patient completes 3 months of follow up. A second analysis will be conducted when all patients have completed 12 months of follow up. The final analysis will occur when the final patient completes 36 months of follow up.

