### **2.3.3.1 CLN-PRO-V002 Study Results (24 M)**

Recruitment began in October 2013 and was completed in June 2014 with 20 patients implanted. Thirteen patients completed the 2 year follow up visit. Of the 7 patients terminating the study early, 3 died and 4 were withdrawn after occlusion of the HAV. None of the deaths were considered related to the investigational device or procedure.

Kaplan-Meier analyses in which deaths were censored revealed primary, primary assisted, and secondary patency probability rates of 79.2%, 79.0%, and 89.5% at Week 26, 63.3%, 63.2%, and 84.2% at Month 12, 63.3%, 63.2%, and 79.0% at Month 18, and 58.1%, 57.9%, and 73.7% at Month 24.

Six patients (30%) required at least 1 graft intervention to maintain or restore HAV patency during the study. Four patients required 1 intervention and 1 patient each required 3 and 4 interventions. Most interventions successfully restored patency. However, in 1 patient the graft patency could not be restored and the HAV was replaced with an alternative bypass graft. Two patients, who had previously undergone successful interventions, developed a recurrent thrombosis which was not treated and the HAV was left occluded. Two patients experienced HAV thrombosis with no or minimal symptoms and refused interventions on the HAV.

All 20 patients experienced AEs (a total of 92 events). Thirty-one of these events in 13 patients were considered serious. The most frequent AEs reported included graft thrombosis (35% of patients), anastomotic stenosis (20% of patients), lymphocele (20% of patients), and local swelling (15% of patient). Those serious adverse events (SAEs) reported by at least 2 patients were graft thrombosis (6 patients, 30%) and anastomotic stenosis (2 patients, 10%).

No patient showed an increase in PRA levels. Two patients had a significant (> 2 fold) increase from baseline in IgG levels. One of these patients experienced a thrombosis of the HAV between 3 and 6 months after implantation, while the other patient has had no HAV-related AEs and continues to have primary patency. Neither patient has had any evidence of dilatation or structural degeneration of the HAV.

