### **2.2.1.2 Primary Efficacy Endpoints – assessed at 3 months post implantation**

- Primary patency
  - Defined as being maintained until any intervention designed to maintain or reestablish patency, access thrombosis or the measurement of patency', i.e., patent without interventions
- Primary assisted patency
  - Defined as being maintained until access thrombosis or the time of measurement of patency, including intervening manipulations (surgical or endovascular interventions) designed to maintain the functionality of patent access' i.e., patent without an intervention to clear a thrombus
- Secondary patency
  - Defined as being maintained until access abandonment
  - Access abandonment defined as no remaining segment of the study conduit is incorporated into the vascular access circuit used for dialysis

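### SAP 6.2 adds an undefined success condition to the intervention endpoint; read literally, with the abandonment-date rule in SAP 4.4.1, it leaves out failed salvage sessions and slightly understates the intervention burden

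*SAP*

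**What the plan says.** The Protocol Summary, Protocol 4.2.2.2 and SAP 2.2.2.2 all list the endpoint in the same terms: "Interventions required to achieve/maintain secondary patency". This defines it by purpose and sets no condition on outcome.

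SAP 6.2 opens by saying that analyses of patency and "intervention rate through 36 months of follow-up will be carried out on the ITT set", again with no outcome condition. It counts everything done at one session as one intervention. It then leads into four items with "Summaries for interventions required that successfully achieved/maintained Secondary Patency will include". The items are the number per subject, the rate, the reasons and the procedure types. The rate is sessions per subject per year for as long as the HAV has not been abandoned, reported to Month 12 and overall.

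Three other SAP sections bear on this:

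- **SAP 2.2.1.2** on secondary patency: "Defined as being maintained until access abandonment".
- **SAP 4.4.1**: if the decision to abandon comes late, for example after a delayed thrombectomy that fails, abandonment is dated to when the thrombosis was first recognised.
- **SAP 6.3**: total interventions are analysed by site and by gender, with no success term.

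**The concern.** The lead-in turns an endpoint about need into one about result. A session that tries to rescue a HAV and ends in its abandonment was required to maintain secondary patency but did not maintain it. On the literal wording it is not counted, while the patent time of that HAV before abandonment stays in the rate's denominator. The SAP gives no criterion, time point or assessor for success, so a programmer has to guess.

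The sessions at risk belong to the HAVs that were lost. For a given denominator, leaving them out can only lower the reported burden. That matters somewhat because the intervention count gives context to secondary patency, and Protocol 2.5.2 names fewer interventions as a possible benefit.

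**Working it through.** The documents give no figure for this point, so there is nothing to reproduce. The check compares the texts and then illustrates the size.

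**1. Which sessions are affected**

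| Session | Literal SAP 6.2 lead-in | Rate window with SAP 4.4.1 |
|---|---|---|
| Restores or keeps patency | counted | inside |
| Fails, a later session succeeds | not clearly excluded, since secondary patency runs to abandonment | inside |
| Fails without delay, HAV abandoned | excluded | not clearly outside |
| Delayed, fails, HAV abandoned | excluded | outside, because abandonment is backdated |

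For the last row, deleting the success term would not bring the session back into the rate.

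**2. The programme's own example**

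Protocol 2.3.3.1 covers the arterial bypass study, a different population. It reports sessions by need and then names the failure separately: "Four patients required 1 intervention and 1 patient each required 3 and 4 interventions", followed by "Most interventions successfully restored patency. However, in 1 patient the graft patency could not be restored".

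- Sessions: 4×1 + 3 + 4 = 11.
- If exactly one session failed and it is among the 11, the literal SAP 6.2 wording would drop 1/11 = 9.1% (exact 95% CI 0.2 to 41%).
- Lost HAVs described: 1 not restored; 2 whose patients "developed a recurrent thrombosis which was not treated and the HAV was left occluded"; and 2 more ("Two patients experienced HAV thrombosis with no or minimal symptoms and refused interventions on the HAV"). That is 5 losses and 1 failed session, or 0.2 per loss.

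**3. This study to Month 12**

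Inputs:

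- N = 30, the planned maximum (Protocol Summary).
- Secondary patency 97% at 6 months and 91% at 12 months in the two earlier dialysis studies (Protocol 2.3.2.1), joined by straight lines from 100%.
- Assumed: no other censoring; f = 0 to 1 failed session per abandonment; r = 1 to 3 successful sessions per patent-year.

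Results:

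- Abandonments: 30 × (1 − 0.91) = 2.7.
- Patent time: 30 × [0.5 × (1 + 0.97)/2 + 0.5 × (0.97 + 0.91)/2] = 30 × 0.9625 = 28.875 patient-years.
- Omitted rate: m = 2.7f / 28.875.
- Shortfall: m / (m + r).

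| f | Sessions omitted | m per patient-year | r = 1 | r = 2 | r = 3 |
|---|---|---|---|---|---|
| 0 | 0 | 0 | 0% | 0% | 0% |
| 0.2 | 0.54 | 0.019 | 1.8% | 0.9% | 0.6% |
| 0.5 | 1.35 | 0.047 | 4.5% | 2.3% | 1.5% |
| 1 | 2.7 | 0.094 | 8.6% | 4.5% | 3.0% |

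These shortfalls combine the lead-in and the backdating rule. The documents do not allow the two to be separated.

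**4. Against sampling noise**

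The relative Poisson standard error with f = 1 is 1/√(28.875 + 2.7) = 17.8% at r = 1, and 1/√(86.625 + 2.7) = 10.6% at r = 3. Every shortfall in the table is smaller than the standard error at the same r.

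**The case against.** The strongest reply is that this is clumsy drafting rather than a restriction. The lead-in keeps the idea of interventions being required, the rate item carries its own definition without a success term, and the opening sentence of 6.2 has none either. The fourth item is a complete sentence of its own and can be read as counting every thrombectomy, angioplasty and stent. Total interventions in SAP 6.3 most naturally means all of them, and adding the two sites gives a study total. The losses are also visible elsewhere: the Kaplan-Meier analysis, reasons for abandonment in SAP 7.6, thrombosis and clinically significant stenosis in 7.2.6, and the intervention listings in 7.7.

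Most of this stands, and it limits the point. It does not remove it. The endpoint and its analysis still differ in wording, and Protocol 2.3.3.1 uses the same success term to separate sessions that worked from one that did not. SAP 6.3 does not say whether it inherits the 6.2 definition, so its totals may disagree with 6.2. SAP 7.7 leaves intervention summaries to discretion.

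A reader might infer three stronger things that the documents do not support:

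- **That every failed procedure is discarded.** A failed session followed by a successful one is not clearly excluded, because secondary patency continues until abandonment.
- **That one word causes the whole shortfall in the rate.** For delayed failures, SAP 4.4.1 takes the session out of the rate window whatever the lead-in says.
- **That failures are hidden from the report.** The intervention data are listed, and the losses are tabulated.

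**Conclusion.** The point holds as a minor mismatch and ambiguity. SAP 6.2 puts an undefined success condition on an endpoint that has none. On the literal reading, failed sessions ending in abandonment leave the number, rate and reasons summaries, and arguably the procedure types. SAP 4.4.1 separately removes delayed failures from the rate.

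Any bias is downward: about 0 to 9% of the Month 12 rate, both causes combined. That range rests on N = 30, the earlier dialysis patency figures, no other censoring, and assumed values of 0 to 1 failed session per abandonment and 1 to 3 successful sessions per year. The bypass figure of 0.2 falls inside the assumed range for failed sessions but is a weak guide to dialysis access. The bias is zero if no attempt precedes abandonment. It is below sampling noise, and the endpoint is descriptive with no test or comparator, so no study conclusion depends on it.

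**What to change.** Amend the SAP in three places:

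1. **6.2 lead-in.** Restore the endpoint's own terms: the summaries cover every session performed to achieve or maintain secondary patency, whether or not it succeeded.
2. **6.2 rate item.** State that the numerator is all such sessions, including a failed session leading to abandonment even if it falls after the abandonment date assigned under 4.4.1. Keep the denominator as time from implantation to abandonment or censoring.
3. **6.3.** State that total interventions uses the same definition, so that subgroup and overall counts agree.

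Optionally, also report the number of sessions that ended in abandonment, defined as those after which the HAV was not used again before recorded abandonment.

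The cost is SAP wording only. Procedures and their reasons are already recorded (Protocol 8.5.1.5), as is the outcome of interventions for Events of Special Interest (Protocol 8.3.8). The downside is a slightly less favourable rate.

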### **6.3 Prognostic Factors and Subgroup Analyses**

No analyses based on prognostic factors are planned for the study.

The following subgroup analyses will be performed:

- Primary, primary assisted, and secondary patency by gender.
- Primary, primary assisted, and secondary patency by study site.
- Total interventions by study site, and by gender.

The analysis listed above will be performed for each subgroup. For example, the K-M analysis will be performed including only male subjects, and then will be repeated including only female subjects.

## **7. SAFETY ANALYSIS**

Safety data include results from laboratory testing (clinical chemistry, hematology, anti-HAV IgG antibodies, and PRA), adverse events, findings from symptom directed physical exams and Duplex ultrasound results. All safety summaries (or analyses if applicable) will be conducted using the Safety analysis set.

Screening laboratory testing will include International Normalized Ratio (INR) or Prothrombin time, and a serum or urine pregnancy dipstick test for women of childbearing potential in order to help ensure the eligibility and safety of prospective subjects.

### **7.1 Extent of Exposure**

There are two exposures that will be summarized:

1. Subject exposure during the study period is defined as the length of time from implant to explant, death or early termination (e.g. lost to follow up, withdrew consent etc.).

2. Subject exposure to a patent HAV used for hemodialysis is defined as the length of time from first cannulation to explant, abandonment, death, transplant, or early termination (e.g. lost to follow up, withdrew consent etc.).

Subject exposure during the study period and exposure to a patent HAV used for hemodialysis will be reported at each analysis time point. Descriptive statistics will be provided for days of exposure. Overall exposure will be summarized in total subject-years. This will be calculated as follows:

Exposure in subject-years = Sum of duration of exposure in days (for all enrolled subjects) / 365.25.

## **7.2 Adverse Events**

An AE is defined as any untoward medical occurrence in a subject administered an IMP or has undergone study procedures and which does not necessarily have a causal relationship with this treatment. An AE can therefore be any unintended sign (including an abnormal laboratory finding), symptom, or disease temporally associated with the use of the IMP, whether or not related to the IMP.

During the Screening period (Day -45 to Day 0 prior to implantation), only SAEs related to study procedures will be reported beginning at the time the subject signs the informed consent form. From Day 0 after implantation to one-year post-implantation (Month 12 visit) or ET visit, whichever occurs earlier, all AEs will be reported.

During the long-term follow-up period from 1 year to 3 years post-implantation, only the following will be reported by the investigator:

- All related SAEs
- All Events of Special Interest as defined in Protocol Section 9.3

### **7.2.1 Treatment-emergent Adverse Events**

AEs will be summarized as treatment-emergent AEs (TEAEs) for the Safety analysis set.

An AE will be considered a TEAE if the onset of the event is on or after the start of the anesthesia for the implant surgery. If an AE start date is completely missing, then the AE will be considered as TEAE unless it can be determined that the AE end date occurred prior to the anesthesia for the implant surgery. If the AE start date is partially missing then the start date will be imputed as described in Section 4.4.2.

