## 9.6 Reporting of Adverse Events

At each evaluation, the subject will be questioned in a general way and no specific symptoms will be suggested. If any AEs have occurred, they will be recorded on the AE pages of the eCRF and in the subject's medical record. If known, the diagnosis should be recorded in preference to the listing of individual signs and symptoms.

During the Screening period (Day -45 to Day 0 prior to implantation), only SAEs related to study procedures will be reported beginning at the time the subject signs the informed consent form. From Day 0 after implantation to 1 year post-implantation (Month 12 visit) or ET visit, whichever occurs earlier, all AEs will be reported.

During the long-term follow-up period from 1 year to 3 years post-implantation, only the following will be reported by the investigator:

- All related SAEs
- All Events of Special Interest (as defined in [Section 9.3](#)).

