3: If adequate vessel mapping has been undertaken within the 8 weeks prior to the start of Screening and there has been no significant change in the condition of the subject (including insertion of CVC) then repeat vessel mapping is at the discretion of the Principal Investigator. Vessel mapping performed by ultrasound in the clinic by the investigator is acceptable.

4: After review by the Principal Investigator, the subject's Screening eCRFs will be provided to the Medical Monitor for review and confirmation of eligibility prior to implantation.

5: Labs include hematology and chemistry. Screening labs will also include INR (or PT if INR value not available) and a serum or urine pregnancy dipstick test for women of childbearing potential. Standard of care laboratory evaluations conducted prior to consent may be used for determination of eligibility provided they are within the screening period time window.

6: Intraoperatively or immediately post-surgery and at Day 7-15, the investigator should use his/her preferred method to confirm patency and adequate flow in the HAV. At all other timepoints, duplex ultrasound will be used to assess patency, diameter of the lumen mid-conduit and flow rate and to monitor aneurysm development. After Month 12, a duplex ultrasound is to be performed at Month 24 and 36.

7: Beginning on Day 28, the investigator may evaluate the HAV to determine if it is suitable to be used for dialysis.

8: Only SAEs related to the screening procedures will be reported during the Screening period. All AEs will be reported from Day 0 after implantation up to the Month 12 visit. After the Month 12 visit up to Month 36, only the following will be reported by the investigator:

- All SAEs considered related to the HAV
- All Events of Special Interest.

9: Subjects will be assessed at a study visit that can occur anytime from Day 7 to 15.

10: Subjects withdrawn prior to the Month 36 visit will have ET assessments performed. Patients withdrawn prior to Month 12 should complete an ET that correlates with the procedures at Month 12. Patients withdrawn after Month 12 and prior to Month 36 should complete an ET visit that correlates with procedures post Month 12 through Month 36.

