## 4.2 Analysis Sets

The following three analysis sets will be defined for this study:

- **Intent-to-Treat (ITT) set:** The ITT set will include all enrolled subjects. The efficacy analysis will be based on the ITT set.
- **Per Protocol (PP) set:** The PP set is defined as all enrolled subjects in whom a HAV has been implanted and in whom there were no major protocol violations. Major protocol violations which would exclude a subject from the PP set will be defined by the sponsor prior to the database lock. Any protocol violation arising during the study which might have a substantial impact on the evaluation of efficacy or safety of HAV and which was not pre-specified as major, will be reviewed by Humacyte who will decide if the subject should be excluded from the PP set. If the number of subjects in the ITT set is different from that in the PP set, efficacy analysis on HAV patency will be repeated in the PP set.
- **Safety analysis set:** The Safety analysis set will include all enrolled subjects in whom a HAV has been implanted. The safety analysis will be conducted in the Safety analysis set.

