#### **7.2.5 Adverse Event Summaries**

All AEs (serious and non-serious) occurring following the HAV implantation, regardless of relationship to the IMP, will be included and classified by SOC and PT using the current MedDRA.

For TEAEs, the following will be summarized and presented for the Safety analysis set:

- i. An overall summary of TEAEs, which includes:
    - a. the number and percentage of subjects experiencing a TEAE
    - b. the number and percentage of subjects experiencing a TEAE by strongest relationship to IMP
    - c. the number and percentage of subjects experiencing a TEAE by strongest relationship to study procedure(s)
    - d. the number and percentage of subjects experiencing a treatment emergent SAE (TESAE)
    - e. the number and percentage of subjects experiencing a TEAE leading to outcome of death
  - ii. the number and percentage of subjects experiencing a TEAE by SOC and PT
  - iii. the number and percentage of subjects experiencing a TEAE by SOC, PT and the strongest relationship to IMP
  - iv. the number and percentage of subjects experiencing a TEAE by SOC, PT and the strongest relationship to study procedure(s)
  - v. the number and percentage of subjects experiencing a TESAE by SOC and PT
  - vi. the number and percentage of subjects experiencing a related TESAE by SOC and PT
  - vii. the number and percentage of subjects experiencing a TEAE leading to outcome of death
-

by SOC and PT

A subject with more than one type of TEAE in a particular SOC will be counted only once in the total of subjects experiencing TEAEs in that particular SOC. Since a subject could have more than one type of TEAE within a particular SOC, the sum of subjects experiencing different TEAEs within the SOC could appear larger than the total number of subjects experiencing TEAEs in that SOC. Similarly, a subject who has experienced a TEAE in more than one SOC will be counted only once in the total number of subjects experiencing AEs in all SOCs.

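### Treatment-emergent AEs are counted from anesthesia, but all-AE reporting starts only after implantation, so non-serious events in between need not be recorded

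*SAP*

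**What the plan says.** **Counting rule.** Under SAP 7.2.1 an AE is treatment-emergent if "the onset of the event is on or after the start of the anesthesia for the implant surgery".

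**Collection rule.** Protocol 9.6 says: "From Day 0 after implantation to 1 year post-implantation (Month 12 visit) or ET visit, whichever occurs earlier, all AEs will be reported". SAP 7.2 repeats this almost word for word. Footnote 8 of the visit schedule (Protocol Appendix 1, repeated in SAP Appendix A) says: "All AEs will be reported from Day 0 after implantation up to the Month 12 visit". Protocol 9.6.1 starts the 24-hour reporting of SAEs, whatever their cause, at the same point. SAP 7.2.5 opens by including "All AEs (serious and non-serious) occurring following the HAV implantation".

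**Before implantation.** Protocol 9.6 says: "During the Screening period (Day -45 to Day 0 prior to implantation), only SAEs related to study procedures will be reported", and SAP 7.2 agrees. Footnote 8 is narrower: "Only SAEs related to the screening procedures will be reported during the Screening period". Protocol 8.1.11 also refers to screening procedures only.

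**Analysis set.** SAP 4.2 says: "The Safety analysis set will include all enrolled subjects in whom a HAV has been implanted". SAP 7 bases every safety summary on that set.

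**The concern.** The counting rule covers an interval that the collection rule leaves out. Both Protocol 9.6 and SAP 7.2 divide Day 0 into a part before and a part after implantation, so the cut falls inside the day of surgery. Between anesthesia and implantation a site that follows the protocol has no duty to enter a non-serious event as an AE, although the SAP means to count it. The documents clearly want perioperative events: the AE definition includes people who have undergone study procedures, Protocol 9.4 asks for a separate causality judgement against the index operation, and SAP 7.2.5 tabulates TEAEs by relationship to procedure.

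At stake is the completeness of the primary safety tables in a study whose purpose is to confirm the safety of HAVs from a new manufacturing process. The results are purely descriptive, so the counts are the findings. Two sites that read *implantation* differently could also record the same event differently. For serious events, Protocol 9.8 has SAEs suggesting mechanical failure passed to the DMC chair, which presupposes that they were reported.

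**Working it through.** The plan gives no figure on this point, so the check is mainly a comparison of texts.

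**Step 1. Counting against collection, by type of event.**

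| Event | Treatment-emergent under SAP 7.2.1? | Must it be reported? |
|---|---|---|
| Non-serious, from anesthesia to implantation | Yes | No |
| Serious and procedure-related, same interval | Yes | Yes under Protocol 9.6 and SAP 7.2; no under Protocol 8.1.11 and footnote 8, unless related to screening procedures |
| Serious, judged unrelated to procedures, same interval | Yes | No |
| Any AE after implantation, up to Month 12 or early termination | Yes | Yes |
| Non-serious, subject operated on but never implanted | Yes by onset, but the subject is outside the Safety set | No, because the start of all-AE reporting is never reached |

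**Step 2. Where the loss occurs.** SAP 4.3 computes study days from dates, and the AE listing in SAP 7.2.5 carries date and day of onset. An event dated Day 0 that is recorded as an AE would therefore normally be tabulated. The gap is at recording.

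**Step 3. Anastomotic bleeding.** This is a listed component of the primary safety endpoint. It requires a sewn anastomosis.
- If *implantation* means that the HAV is in place, bleeding at first flow falls after implantation and is reportable.
- If it means that the operation is complete, non-serious bleeding on the table falls before it and is not.

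No section defines the word.

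**Step 4. What else captures Day 0 events.**
- Protocol 8.2.4 requires immediate postoperative complications to be documented; the schedule row is wider and covers any complication.
- The schedule marks AEs and events of special interest at Day 0, subject to footnote 8.
- Protocol 8.2.6 questions the subject about health and HAV problems and defers to Section 9.
- SAP 7.7 lists complication data and summarises them only where judged appropriate.

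These leave a trace, but none requires a non-serious intraoperative event to be entered as an AE.

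**Step 5. Scale.** Input: up to 30 implanted subjects (Protocol Summary). Exact Clopper-Pearson 95% intervals for x events in n subjects: the lower limit is the 2.5% quantile of Beta(x, n − x + 1), set to 0 when x = 0; the upper limit is the 97.5% quantile of Beta(x + 1, n − x).
- 0/30 = 0%, interval 0 to 11.6%.
- 1/30 = 3.3%, interval 0.1 to 17.2%.
- If one attempted but non-implanted subject with an event were added to 30 implanted: 1/31 = 3.2%, interval 0.1 to 16.7%.

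The documents give no intraoperative event risk. Assuming a risk p per subject, the chance of at least one such event in 30 is 1 − (1 − p)^30:
- p = 1%: 26%
- p = 2%: 46%
- p = 5%: 79%
- p = 10%: 96%

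**The case against.** The strongest reply is that little is really lost. On a natural reading the HAV is implanted once it is sewn in, so bleeding at first flow is already inside the collection period. What remains is non-serious events before placement, which say little about the vessel's strength. Anastomotic bleeding and rupture are events of special interest with no start time in their definition (Protocol 9.3), and the same section asks for iatrogenic injuries to be reported as AEs. Day 0 complications are documented and listed. The opening sentence of SAP 7.2.5 concerns inclusion and coding; the tables under it are for TEAEs and so follow SAP 7.2.1. A Safety set of implanted subjects fits a primary objective framed as safety after implantation, and other enrolled subjects stay in the ITT disposition and deviation tables.

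Most of this stands as a limit on the consequence. A reader might infer that intraoperative anastomotic bleeding is excluded outright; the documents do not support that, because it depends on an undefined word. A reader might also infer that such events vanish altogether, whereas surgical records and listings may still show them. Nor do the documents support a claim that zero or one event is the likely total for the mechanical-failure endpoint: they give no rate for intraoperative events, and Protocol 2.3.2.1 mentions small pseudoaneurysms, which belong to the same endpoint.

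The reply does not remove the mismatch between counting and collection or the conflict over pre-implantation SAEs. Nor does it supply a safety summary for subjects who were operated on but not implanted.

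**Conclusion.** The inconsistency is certain from the text; its effect is probably small and cannot be sized from the documents. Non-serious AEs between anesthesia and implantation need not be recorded and so can be missing from the TEAE tables. Reporting of SAEs in the same interval depends on which section a site follows. Subjects anesthetised but not implanted enter no safety summary table.

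With 30 subjects, each unrecorded event is worth 3.3 percentage points on a reported rate. Whether any occurs is unknown, and the 26% to 96% range rests on assumed risks of 1% to 10%. Restricting the Safety set to implanted subjects is a defensible choice. The weakness is that nothing reports the others alongside it.

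**What to change.** 1. Start collection of all AEs and SAEs at the start of anesthesia for the implant operation, in Protocol 9.6, 9.6.1 and footnote 8, and in SAP 7.2, SAP 7.2.5 and SAP Appendix A.
2. Define *implantation*, for example as the first anastomosis having been begun, and use it throughout.
3. Reconcile *study procedures* (Protocol 9.6, SAP 7.2) with *screening procedures* (Protocol 8.1.11, footnote 8) for SAEs before that start.
4. Keep the Safety set, and add a separate summary of AEs in any subject in whom implant surgery was started but no HAV was left in place.

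The cost is protocol and SAP wording. No visit or test is added, since Day 0 already has an AE assessment (Protocol 8.2.6). The safety counts may look slightly less favourable.
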